14.3.1 Prior to Each Transfusion Episode

Blood Product Procedures

1. Collect specimen from each unit prior to the transfusion (Section 16.1)
 - a. Local: Complete Blood Count (CBC)
 - b. Central: supernatant potassium, supernatant sodium, and supernatant hemoglobin

Subject Procedures

1. Measure weight
2. Conduct physical examination (only prior to the first transfusion of Treatment Period 2)

- a. Perform an abbreviated physical examination, including examination of general appearance, eyes/ears/nose/throat, pulmonary/chest, cardiovascular, abdominal, and neurological
3. Record vital signs within 1 hour prior to transfusion. Vital signs include HR, BP, RR, SpO₂, and temperature
4. Local Laboratory Tests (may be collected/tested at any time within 5 days before the transfusion unless otherwise noted)
 - a. Prior to Treatment Period 2 only: Serum or urine pregnancy test; not required if female subjects are not of child-bearing potential (ie, prior to menses onset, surgically sterilized, 1-year postmenopausal)
 - b. Routine blood typing and crossmatch per site standard practice
 - c. RBC antibody screen
 - o If positive, conduct RBC antibody identification and record only new RBC antibodies, if applicable
 - d. Crossmatch with RBCs derived from Mirasol-treated WB if the previous study transfusion was a MIR RBC product
 - e. CBC, plasma free hemoglobin; and haptoglobin within 1 hour prior to transfusion (Section 16.2.1)
 - f. Chemistry within 1 hour prior to transfusion (Section 16.2.1)
5. Collect blood from subject for Central Laboratory Tests (Section 16.2.2)
 - a. Collect and hold blood sample for RBC antibody testing, when the antibody screen and crossmatch performed at the local lab either is positive for an antibody specific to MIR-treated RBCs or inconclusive. See Section 16.2.2.1 for details regarding criteria for sending samples to the central laboratory
 - b. Collect blood sample for HLA testing, only during Treatment Period 1 (Section 16.2.2.2)
6. Record all concomitant medications taken starting from the day of the first study transfusion and throughout the study, including all blood products transfused (eg, off-protocol RBCs, platelets) (Section 17)
7. Record AEs, SAEs, and UADEs (Section 19). All AEs will be recorded from the time of the first study transfusion through the final follow-up or early termination visit

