14.3.2 During and Within 15 Minutes Post-End Transfusion

1. Begin RBC transfusion per site standard procedures

Note: As per the AABB Technical Manual, the initial flow rate for RBC transfusions should be 1-2 mL/min (60-120 mL/hr) for the first 15 minutes, with the total infusion duration \leq 4 hours⁴¹

2. Record start/end date/time(s) of transfusion(s)
3. Record volume of RBCs transfused
4. Record vital signs (HR, BP, RR, SpO₂, temperature) during transfusion at 15 (\pm 5) minutes after starting transfusion and hourly, at end of transfusion, and 15 (\pm 5) minutes after end of transfusion. A \pm 15 minute window is allowed unless otherwise specified
5. Collect blood for Local Laboratory Tests at 15 (+ 5) minutes post-end transfusion
 - a. CBC, plasma free hemoglobin and haptoglobin (Section 16.2.1)
 - b. Serum potassium and sodium concentrations
6. Record concomitant medications and all blood products transfused (eg, off-protocol RBCs, platelets) (Section 17)
7. Record AEs, SAEs, and UADEs (Section 19)

14.3.3 1 Day (24 \pm 6 hours) Post-Transfusion

1. Record vital signs (HR, BP, RR, SpO₂, temperature)
2. Collect blood for Local Laboratory Tests
 - a. CBC, plasma free hemoglobin and haptoglobin (Section 16.2.1)
 - b. Chemistry (Section 16.2.1)
3. Record concomitant medications and all blood products transfused (eg, off-protocol RBCs, platelets) (Section 17)
4. Record AEs, SAEs, and UADEs (Section 19)

14.3.4 7 Days (\pm 1 day) Post-Transfusion

1. Collect blood for Local Laboratory Tests
 - a. CBC and haptoglobin (Section 16.2.1)
 - b. Chemistry (Section 16.2.1)
 - c. RBC antibody screen
 - o If positive, conduct RBC antibody identification and record only new RBC antibodies, if applicable
 - d. Crossmatch with Mirasol-treated RBCs if the previous study transfusion was a MIR RBC product
2. Collect blood for Central Laboratory Tests (Section 16.2.2)
 - a. Collect and hold blood sample for central RBC antibody testing, when the antibody screen and crossmatch performed at the local lab either is positive for an antibody

specific to MIR-treated RBCs or inconclusive. See Section 16.2.2.1 for details regarding criteria for sending samples to the central laboratory

3. Record concomitant medications and all blood products transfused (eg, off-protocol RBC, platelets) (Section 17)
4. Record AEs, SAEs, and UADEs (Section 19)

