19.3 Potential Risk of the Mirasol System for Whole Blood

The risk of using the Mirasol System incorrectly is minimized by an inherently safe design. The disposable kit comes prefilled with the correct dose of riboflavin and sterility is maintained throughout the process. The Illuminator has built-in safety features, including visual and auditory alarms that ensure correct illumination. The Mirasol Manager Software prevents the risk of double illumination. Labeling prevents the risk of illumination by the Mirasol System and further irradiation.

Mirasol System treatment of blood or blood components has been evaluated for hemocompatibility, cytotoxicity, genotoxicity, immunotoxicity, and embryo-fetal development both in vitro and in vivo in several animal species. These nonclinical studies have shown no observable or Mirasol-related changes to the toxicity profile. Terumo BCT has extensively evaluated the toxicological profile of riboflavin, its photoproduct (lumichrome), and blood products treated by the Mirasol System in several in vivo and in vitro studies.⁴⁴ Three (3) potential risks have been identified that are related to blood quality: putative toxic effects of riboflavin and its photoproduct, potential for transient hyperkalemia due to increased extracellular potassium in RBCs derived from Mirasol-treated WB, and the reduced survival which may impact the need for more frequent RBC transfusions.

Mirasol-treated products are not to be administered in the event massive transfusion is warranted.

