21.9.2 Laboratory Tests

All laboratory values will be converted to International System of Units (SI units).

Laboratory test covered by the CTCAE (version 4.03) will be assigned grades accordingly. A grade of 0 will be assumed for non-missing values not graded as 1 or higher. In the unlikely cases where a laboratory normal range overlaps in the higher (ie, non-zero) CTCAE grade, the

laboratory value will still be taken as within normal limits and assigned a CTCAE grade of 0. Grade 5 will not be used.

For laboratory tests where grades are not defined by CTCAE, results will be graded by the low/normal/high classifications based on normal ranges.

The following summaries by treatment group will be presented separately for laboratory parameters: change from baseline to the time point prior to each transfusion and change from the pre transfusion time point between each consecutive transfusion.

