## **VI. General Analytical Considerations**

### **A. Study Time Points**

#### Baseline

Baseline for analysis purposes is defined as the last assessment prior to treatment start date/time (or randomization date, for patients who never receive any treatment) for each treatment period. In cases where the date is the same and the times are unknown, assessments taken on the same day are considered baseline.

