## **B. Clinical Laboratory Results**

All laboratory values will be converted to International System of Units (SI units).

Laboratory test covered by the CTCAE (version 4.03) will be assigned grades accordingly. A grade of 0 will be assumed for non-missing values not graded as 1 or higher. In the unlikely cases where a laboratory normal range overlaps in the higher (ie, non-zero) CTCAE grade, the laboratory value will still be taken as within normal limits and assigned a CTCAE grade of 0. Grade 5 will not be used.

For laboratory tests where grades are not defined by CTCAE, results will be graded by the low/normal/high classifications based on normal ranges.

The following summaries by treatment group will be presented separately for laboratory parameters: shift in CTCAE grade from pre-transfusion of wash-in period to each assessment timepoint for laboratory tests that are graded; for non-graded tests, shift in normal range classification from pre-transfusion of wash-in period to each assessment timepoint. For both shift tables, a summary of worst shift from pre-transfusion of wash-in period will be presented.

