#### **C. Vital Signs**

Vital signs will be performed at baseline, during and within 15 min post-transfusion, 1 Day post-transfusion, and 7 Days post-transfusion. Vital signs include temperature, heart rate (HR), respiratory rate (RR), blood pressure (BP), and arterial oxygen saturation via pulse oximetry (SpO2), will be listed by treatment sequence, treatment group and time point. Vital signs will be summarized as actual and change from baseline for each treatment group at each scheduled assessment.

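### SAP IX.B reports laboratory values only as grade or range shifts from a wash-in sample, so the within-episode rise in serum potassium is never estimated by product

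*SAP*

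**What the plan says.** SAP IX.B lists the laboratory summaries. Graded tests get "shift in CTCAE grade from pre-transfusion of wash-in period to each assessment timepoint"; non-graded tests get the same shift in low/normal/high class; both get a worst-shift summary. On grading, "A grade of 0 will be assumed for non-missing values not graded as 1 or higher", and a value inside the laboratory's normal range counts as grade 0 even where the CTCAE scale would grade it higher. The section names no mean, no actual value and no continuous change. The next section does for vital signs: "Vital signs will be summarized as actual and change from baseline for each treatment group at each scheduled assessment".

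The reference sample is not defined in IX.B. SAP VI.A defines baseline once per treatment period: "Baseline for analysis purposes is defined as the last assessment prior to treatment start date/time".

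The protocol's schedule gives a potassium pair around each transfusion. Section 14.3.1 requires "Chemistry within 1 hour prior to transfusion", and section 16.2.1 puts potassium in the chemistry panel. Section 14.3.2 adds "Serum potassium and sodium concentrations" at 15 minutes after the end of transfusion. Protocol 21.9.2 planned laboratory change from baseline to the point before each transfusion, and "change from the pre transfusion time point between each consecutive transfusion". Neither summary is carried into the SAP.

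Protocol 16.1 has each red cell unit tested before transfusion so that in vitro findings can be related to in vivo ones. Section 16.1.2 names supernatant potassium and gives a formula for percent hemolysis. Neither quantity appears in protocol section 21 or in any SAP analysis.

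**The concern.** Protocol 19.3 lists three blood-quality risks of the device. One is the "potential for transient hyperkalemia due to increased extracellular potassium in RBCs derived from Mirasol-treated WB". The schedule is well suited to measuring it: at 15 minutes the chemistry panel is cut to potassium and sodium alone. The natural quantity is the difference between the two samples of one episode, compared between products within subject.

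A categorical shift from a wash-in sample is a coarse substitute. It hides any rise that does not cross a grade or range limit. Where the reference comes from an earlier visit, it also mixes the effect of the transfusion with drift in potassium between visits. At stake is a descriptive safety result that readers of the trial would expect: how much serum potassium rises after each product. The unit measurements that would help explain such a rise would go unreported as well.

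**Working it through.** The plan states no figure on this point, so there is none to reproduce. The check is a comparison of text, followed by context arithmetic.

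**1. What the SAP does with the 15-minute value.** IX.B covers each assessment timepoint, so the value enters the shift and worst-shift tables. It is classified and never subtracted. The documents do not list which tests are CTCAE-graded. If potassium is not graded, the normal-range shift applies with the same reference, and the point is unchanged.

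**2. Episodes without a same-episode reference.** Inputs: 2-4 week intervals (protocol 11.2), a 50-day wash-in, then two episodes (protocol 10.1).

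| Interval | Transfusion days | Episodes | Reference = first sample of period | Reference = own sample for each wash-in episode |
|---|---|---|---|---|
| 2 weeks | 0, 14, 28, 42, 56, 70 | 6 | 5/6 = 83% lack one | 2/6 = 33% lack one |
| 3 weeks | 0, 21, 42, 63, 84 | 5 | 4/5 = 80% | 2/5 = 40% |
| 4 weeks | 0, 28, 56, 84 | 4 | 3/4 = 75% | 2/4 = 50% |

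The share is 33-83%. On the first reading, the reference for the two efficacy episodes is 56-84 days old. Even an episode that has its own reference gets only a categorical summary.

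**3. Potassium load per unit.** Inputs: means in protocol Table 19-5. Volume = total Hb / Hb concentration x 100; supernatant = volume x (1 - Hct); load = supernatant x potassium.
- Day 21, Mirasol: 50.69/19.16 x 100 = 264.6 mL; x (1 - 0.5666) = 114.7 mL; x 68.42 mmol/L = 7.85 mmol.
- Day 21, control: 52.37/19.35 x 100 = 270.6 mL; x (1 - 0.5774) = 114.4 mL; x 37.35 mmol/L = 4.27 mmol.
- Excess: 3.57 mmol per unit at day 21 (difference taken before rounding). The same steps at day 0 give 0.272 - 0.263 = 0.01 mmol.

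**4. Range for the extra serum rise.** The upper bound assumes two 21-day units, weight 40-70 kg, extracellular volume 0.2 L/kg, full mixing in that volume, and no cell uptake or excretion. None of these is in the documents.
- 70 kg: 2 x 3.57 / (0.2 x 70) = 0.51 mmol/L.
- 40 kg: 2 x 3.57 / (0.2 x 40) = 0.89 mmol/L.

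The lower end is near zero. Protocol 19.3.2 calls 21-day Mirasol potassium similar to that of irradiated units at 28 days and conventional units at 42 days. Table 19-4 gives 72.3 mEq/L for irradiated units at day 28, against 68.42 here, which is no excess. The SAP's analysis of units stored up to 21 days confirms that reference units may be stored up to 42 days.

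**5. What a shift table can miss (illustration).** Assume normally distributed potassium with mean 4.2 and SD 0.35 mmol/L. A mean rise of 0.2 mmol/L moves the share above an upper limit of 5.0 from 1.1% to 4.3%, and above 5.2 from 0.2% to 1.1%. Every subject's potassium has risen on average, but few cross the limit.

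**6. Unit tests.** Protocol 16 separates product testing (16.1) from clinical testing of subjects (16.2). SAP IX.B is headed clinical results, so it does not cover unit potassium or percent hemolysis, and no other section does.

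**The case against.** The strongest reply is that the clinically relevant signal is already covered. The shift tables include the 15-minute sample, and worst shift is tabulated. Protocol 19.5.1 makes an abnormal value an adverse event if it is treated, clinically significant or related. The DMC reviews safety throughout (protocol 20), and the listings in SAP VI.K will show recorded values. A change of 0.1-0.2 mmol/L inside the normal range triggers no decision in either document. All of this stands. A reader might infer that the 15-minute potassium is unused, or that hyperkalemia could go undetected; the documents do not support that.

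A reader might also infer that the SAP abandons a same-episode change promised in the protocol. The wording of 21.9.2 does not settle this. It may mean only successive pre-transfusion samples, or it may include samples taken between two transfusions. On the narrow reading a same-episode change was never planned. On either reading the protocol planned some laboratory change and the SAP has none.

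Finally, the phrase for the reference sample is open. The wash-in holds two to four transfusions, each with its own pre-transfusion sample, and IX.B does not use the word baseline. So 75-83% cannot be stated as fact, which is why the share is given as 33-83%. The correlation purpose of the unit tests is likewise not an objective or endpoint, so a missing correlation model breaks no commitment in the analysis plan.

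What remains is that none of these safeguards estimates the rise by product, although the paired samples to do so are collected at every episode.

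**Conclusion.** The point holds as a minor improvement to SAP IX.B. The plan summarizes laboratory values only by category, from a reference sample it does not define, and gives no estimate of the within-episode potassium rise for a risk that the protocol attributes to the device. That much rests on the text alone.

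The size is uncertain. The share of episodes without a same-episode reference depends on the reading chosen. The extra rise depends on storage age and irradiation of the reference units and on the age of the Mirasol units. Its ceiling of 0.51-0.89 mmol/L also rests on assumed weight, extracellular volume and number of units, and uptake and excretion would lower it. It should not be read as a predicted effect.

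The non-inferiority conclusion on normalized Hb AUC is not touched.

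**What to change.** Keep the shift and worst-shift tables and add to SAP IX.B, as exploratory:

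1. Actual serum potassium at each timepoint, and the continuous change from each episode's own pre-transfusion sample to its 15-minute sample, by product, over all episodes. Fit a mixed model with product, period and episode as fixed effects and subject as a random effect. Report the difference with a 95% confidence interval and no formal test.
2. A sentence stating which sample serves as the wash-in pre-transfusion reference.
3. A descriptive summary of unit supernatant potassium and percent hemolysis by product, with washed units shown separately. Protocol 13.3 records whether a unit was washed, but not whether the test specimen was drawn before or after washing.

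Relating the serum change to potassium load, or unit hemolysis to Hb AUC, is optional and should be labelled descriptive.

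The cost is a few sentences and a few extra exploratory tables, with no new samples or visits. The text should be settled before database lock so that it counts as prespecified.

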19.2 Potential Transfusion Complications in Thalassemia Patients

Thalassemia is the most RBC-transfused syndrome worldwide with as many as 2,000 thalassemia patients estimated to live in the United States. Additionally, there are more than 60,000 births each year of serious forms of thalassemia, globally.⁴ The current standard of care for transfusion-dependent thalassemia patients dictates chronic RBC transfusions with the goal of controlling anemia and suppressing ineffective erythropoiesis.³ Treatment with chronic RBC transfusions requires that these thalassemia patients are exposed to multiple blood products from multiple donors, increasing the risk of TTIs by unscreened or undetected pathogens in the blood supply and transfusion-related immune reactions. In Vichinsky et al., 80% of the thalassemia patients in this study were chronically transfused at the time of enrollment and 24% of transfused thalassemia patients had laboratory evidence of previous exposure to one or more transfusion-associated pathogens.⁴ In this chronically transfused group, patients received an average of 15.6 transfusions during the year prior to enrollment.

Table 19-2: Reported Adverse Reactions in Thalassemia Patients

Adverse Reaction	Description
General Complications	
Hemosiderosis	
 Median ferritin was 1,376 µg/L, 356 µg/L, and 81 µg/L for chronic, intermittent, and nontransfused patients, respectively ($p < 0.0001$) 78% of patients had received chelation therapy
Organ dysfunction	
 16.5% had more than 1 organ system involved Included cardiac disease (13%), gonadal failure (17%), growth hormone deficiency (8%), hypothyroidism (8%), hypoparathyroidism (1%), diabetes (10%), cirrhosis (2%), and thrombotic events (7%)
Thrombotic events	
 Included 6 incidence of pulmonary embolism, 5 superior vena cava syndromes, 4 deep vein thromboses, 3 cardiac thromboses, 2 portal vein thromboses, and 2 renal thrombosis 26 chronic transfusion patients had thrombosis 
 25 of the 26 had a splenectomy 21 of the 26 had concomitant central venous access 31 patients were receiving chronic anticoagulant therapy
Surgical procedures	
 Splenectomy occurred in chronically (52%), intermittently (29%), and nontransfused (7%) patients ($p < 0.0001$) Central venous access (27%) and cholecystectomy (14%) were reported
Infections	

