19.3.2 Risk of Hyperkalemia

Hyperkalemia, high serum potassium, is a recognized risk of RBC transfusions. Many factors may contribute to hyperkalemia, including patient factors (acidosis, hypothermia, hypocalcemia, hyperglycemia, beta-adrenergic blockade, shock/low cardiac output state, low body weight [pediatric]), mode of blood administration (large volume transfusions, rapid administration, central intravenous access administration, pressure infusing devices), and high potassium load in the blood product (due to, eg, excessive hemolysis, long storage time, irradiation).⁴⁵

Mirasol treatment increases extracellular potassium in derived RBC products; the potassium concentration after 21 days of storage (the proposed limit) is similar to what has been observed in gamma-irradiated products after 28 days of storage^{46,47} and in conventional RBCs stored for 42 days (the out date).⁴⁸ Mirasol treated WB and derived RBCs should be used with caution in patients at risk of hyperkalemia (eg, patients with renal failure) and/or requiring administration via central venous access device.

Hyperkalemia is generally transient because of rapid dilution, redistribution into cells and excretion.⁴¹ However, patients with renal failure, premature infants, and newborns receiving large transfusions may be at increased risk for hyperkalemia.⁴¹ Notably, hypokalemia is a more frequent complication of massive RBC transfusion than is hyperkalemia. Transfusion-associated hypokalemia occurs as a result of rapid potassium reuptake in potassium-depleted RBCs; release of aldosterone, antidiuretic hormone and catecholamines; co-infusion of potassium-poor crystalloids; and lowering of potassium due to the metabolism of citrate present in anticoagulants or additive solutions.⁴⁹

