21.2 Reporting Conventions and Definitions

Duration of events will be calculated in days as (stop date – start date + 1). Conversions to weeks, months, or years will be calculated as days/7, days/30.4375, or days/365.25, respectively.

For analysis purposes, baseline will be defined as the day of the first transfusion within each treatment period. In general, missing values will be handled as follows. For continuous variables at baseline, missing values will be excluded from calculation of summary statistics and the number and percent of patients with missing values will be displayed. For categorical values at baseline, the number and percent of patients with missing values will be displayed.

Summary tables of post-baseline measures will be presented by treatment:

- MIR RBCs: RBCs will be derived from WB collected in CPD solution, treated with the Mirasol System for WB, LR, and stored in AS-3 for \leq 21 days at 1 - 6°C
- REF RBCs: LR apheresis RBCs or WB-derived RBCs will be per site standard inventory

Patients will be randomized by treatment sequence: MIR RBCs followed by REF RBCs (MR) or REF RBCs followed by MIR RBCs (RM). Summary tables of baseline measures will be presented by treatment sequence.

Treatment start date is defined within each period as the date of the first transfusion received for each period.

Study day for analysis purposes is defined as (date of event – treatment start date) (+ 1 if the event occurs after treatment start date) within each period.

Baseline for analysis purposes is defined as the last assessment prior to treatment start date/time (or randomization date, for patients who never receive any treatment) for each treatment period. In cases where the date is the same and the times are unknown, assessments taken on the same day are considered baseline.

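### SAP IX.B drops Protocol 21.9.2's laboratory change summaries without explanation and lists only category shifts, which hide most ferritin changes and the size of potassium rises

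*SAP*

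**What the plan says.** Protocol 21.9.2 asks for two laboratory summaries by treatment group: "change from baseline to the time point prior to each transfusion and change from the pre transfusion time point between each consecutive transfusion". Both use pre-transfusion points only.

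SAP IX.B repeats the grading rules that precede that sentence in the protocol, then lists different summaries. For graded tests it gives "shift in CTCAE grade from pre-transfusion of wash-in period to each assessment timepoint for laboratory tests that are graded". For the rest it gives "for non-graded tests, shift in normal range classification from pre-transfusion of wash-in period to each assessment timepoint". For both it adds that "a summary of worst shift from pre-transfusion of wash-in period will be presented". The next section, SAP IX.C, keeps actual values and change from baseline for vital signs.

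The reference point is not new. Protocol 10.1 makes Day 0 of the wash-in the same day as Day 0 of the period, and Protocol 21.2 says "baseline will be defined as the day of the first transfusion within each treatment period". IX.B does not, however, say which wash-in transfusion it means.

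On what is collected:

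- **Before each transfusion.** Protocol 14.3.1 takes chemistry, plasma free Hb and haptoglobin within 1 hour beforehand. Section 16.2.1 places potassium, sodium and ferritin in the chemistry panel.
- **At 15 minutes after the end.** Protocol 14.3.2 takes "Serum potassium and sodium concentrations", with plasma free Hb and haptoglobin.
- **At Day 1.** Protocol 14.3.3 repeats chemistry, plasma free Hb and haptoglobin.

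On the risks: Protocol 19.3 names transient hyperkalaemia as one of three Mirasol risks, and 19.3.2 says "Mirasol treatment increases extracellular potassium in derived RBC products". Iron overload appears in Table 19-1 as a general risk of red-cell transfusion. Table 19-2 reports, for chronically transfused patients, "Median ferritin was 1,376" (µg/L).

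**The concern.** A shift table records a change only when a value crosses a boundary. That matters for two analytes here.

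Ferritin in this population starts far above a normal limit, so a rise stays in the same class. Iron loading is relevant because Protocol 19.3.3 expects that Mirasol recipients may need more transfusions or more units.

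Potassium is sampled on both sides of each transfusion, which allows the transfusion's own effect to be measured. The SAP instead compares the 15-minute class with the period's wash-in value. If that is the first wash-in sample, the reference for the two endpoint transfusions is at least 50 days old. The trial holds the data to estimate the product difference on a risk it names in advance, but no listed table estimates it.

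**Working it through.** The plan states no figure to reproduce. The check is a comparison of the two lists, followed by two illustrations of what a class shift can show.

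**1. The two lists**

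| Item | Protocol 21.9.2 | SAP IX.B |
|---|---|---|
| Change, baseline to each pre-transfusion point | Yes | No; class shift only |
| Change between consecutive pre-transfusion points | Yes | No counterpart |
| 15-minute, Day 1 and Day 7 values | Not named | Yes, as class shift |
| Same-transfusion change, pre to 15 minutes | No | Only at a period's first transfusion, as class shift |
| Actual values | Not named | No |

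The general display rule in SAP VI.K says how continuous data are formatted. It does not say that laboratory values or changes will be tabulated.

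**2. Ferritin: share already high at baseline**

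Input from Table 19-2: median 1,376 µg/L. Assumed: lognormal distribution, upper limit of normal (ULN) 200 to 400 µg/L, log-SD 0.6 to 1.2, no CTCAE grade.

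Formula: P(high) = Φ[ln(1376/ULN) / log-SD].

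| log-SD | ULN 200 | ULN 300 | ULN 400 |
|---|---|---|---|
| 0.6 | 99.9% | 99.4% | 98.0% |
| 0.9 | 98.4% | 95.5% | 91.5% |
| 1.2 | 94.6% | 89.8% | 84.8% |

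A subject at the median who doubled to 2,752 µg/L would be entered as high-to-high.

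**3. Potassium load per unit at Day 21 (Table 19-5)**

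Volume = total Hb / Hb concentration. Supernatant = volume × (1 − Hct). Load = supernatant × potassium concentration.

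- Mirasol: 50.69 / 19.16 = 2.646 dL = 264.6 mL; × (1 − 0.5666) = 114.7 mL; × 68.42 mmol/L = 7.85 mmol.
- Untreated: 52.37 / 19.35 = 2.706 dL = 270.6 mL; × (1 − 0.5774) = 114.4 mL; × 37.35 mmol/L = 4.27 mmol.
- Difference: about 3.6 mmol per unit.

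Assume an extracellular volume of 20% of body weight and no cell uptake or excretion. The excess is then at most 3.57/12 = 0.30 mmol/L per unit at 60 kg, 3.57/8 = 0.45 at 40 kg and 3.57/16 = 0.22 at 80 kg.

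**4. Potassium: share moving from normal to high after a rise d**

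Assumed: pre-transfusion potassium normal with mean 4.2 and SD 0.35 mmol/L. The share is P(K + d > ULN) − P(K > ULN).

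| Rise (mmol/L) | ULN 5.0 | ULN 5.5 |
|---|---|---|
| 0.2 | 3.2% | 0.1% |
| 0.4 | 11.5% | 0.5% |
| 0.6 | 27.3% | 2.3% |
| 1.0 | 70.5% | 19.6% |

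Small and moderate rises mostly leave the class unchanged. Large rises do show. How much of a product difference survives depends heavily on the limit, and normal ranges come from local laboratories (Protocol 16.2.1).

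**The case against.** The strongest replies are these.

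- **A reader might infer that the shift tables cannot show hyperkalaemia. The documents do not support that.** SAP IX.B runs to every assessment timepoint, including the 15-minute sample, and adds worst shift. Protocol 19.5.1 also requires an abnormal value to be recorded as an adverse event if it is clinically significant, is judged related, or leads to an intervention. Rises that cross a limit stay visible. What is lost is magnitude and sub-threshold difference.
- **A reader might infer that the SAP created the potassium gap. It did not.** The protocol's summaries use pre-transfusion points only, so restoring them would not show the 15-minute change. On timepoints the SAP covers more than the protocol.
- **The wash-in reference is the protocol's own period baseline.** This stands, read as the first wash-in sample.
- **Iron overload is not a Mirasol-specific risk.** This stands: Protocol 19.1.2 says so. Transfused load is also analysed directly, because RBC mass infused is a secondary endpoint.
- **The potassium contrast is high-end.** This stands. SAP VIII.B allows REF units stored up to 42 days, and Protocol 10.2 allows irradiated ones. Protocol 19.3.2 likens Mirasol units at 21 days to conventional units at 42 days and irradiated units at 28 days. It also describes rapid dilution, redistribution and excretion.
- **Change in 21.9.2 could mean change of class.** The sentence does follow the grading rules. Even on that reading, the summary between consecutive transfusions has no counterpart in the SAP, and IX.C shows that the SAP specifies actual and change values where it intends them.

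**Conclusion.** The point holds as an unexplained departure from Protocol 21.9.2 that loses descriptive safety information at no saving in data collection. For ferritin the loss is close to complete: about 85% to 99.9% of subjects would start in the top class. For potassium it is partial: rises across a limit are shown, while the size of the rise and sub-threshold product differences are not. The missing same-transfusion comparison is common to both documents.

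These sizes rest on assumptions outside the documents: ferritin limit, spread and lack of a CTCAE grade; serum potassium distribution and limit; body weight; and distribution volume. The 3.6 mmol excess per unit follows from Table 19-5 but applies only to Day-21 Mirasol against Day-21 untreated units.

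It would go too far to conclude that the trial cannot answer its safety question. No primary or secondary efficacy inference is affected, and the values can be tabulated from the collected data. This is a cheap improvement best specified before the analysis.

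**What to change.** In SAP IX.B:

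1. Keep the grade, range and worst-shift tables, and state which wash-in sample is the reference.
2. Restore the two Protocol 21.9.2 summaries by treatment, as actual value and change, or give the reason for dropping them.
3. Add, as a new descriptive summary by product, the change from the same transfusion's pre-value to 15 minutes and, where measured, to Day 1, for potassium, sodium, plasma free Hb and haptoglobin.
4. Summarise ferritin as change or ratio from the first to the last pre-transfusion value within each period, by treatment.

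The cost is SAP wording and a few more descriptive tables. No new samples, visits or hypothesis tests are needed.
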